### **ABBREVIATIONS AND DEFINITIONS OF TERMS**

Abbreviation	Definition
6MWT	6-minute walk test
ACSM	American College of Sports Medicine
AE	Adverse Event
BMI	Body Mass Index
BPNES	Basic Psychological Needs in Exercise Scale
BREQ-2	Behavioral Regulation in Exercise Questionnaire-2
CRF	Cardiorespiratory fitness
CSQ-8	Client Satisfaction Questionnaire
CVD	Cardiovascular Disease
DSC	Data Safety Committee
DSM-V SCID	Structured Clinical Interview for DSM disorders
FDA	Food and Drug Administration
HRR	Heart Rate Reserve
IPAQ	Short Form International Physical Activity Questionnaire
NCPRC	North Carolina Psychiatric Research Center
ОРТМН	Organization of Physical Therapy in Mental Health
PA	Physical Activity
Pace-Life	Targeting Physical Health in Schizophrenia: Physical Activity Can Enhance life
PACES	Physical Activity Enjoyment Scale
PAGEQ	Physical Activity Group Environment Questionnaire
PANSS	Positive and Negative Syndrome Scale PANSS
PAR-Q	Physical Activity Readiness Questionnaire

### Targeting Physical Health in Schizophrenia: Physical Activity Can Enhance life (PACE-Life)

RCT	Randomized Control Trial
RHR	Resting Heart Rate
SAE	Serious Adverse Event
SDT	Self-determination Theory
SSD	Schizophrenia Spectrum Disorder
STEP	Schizophrenia Treatment and Evaluation Program
WAI-SR	Working Alliance Inventory (Group) – Short Form Revised
WASI	Wechsler Abbreviated Scale of Intelligence
WRAT	Wide Range Achievement Test

### **PROTOCOL SYNOPSIS**

Study Title	Targeting Physical Health in Schizophrenia: Physical Activity Can Enhance life (PACE-Life)		
Funder	National Institutes of Mental Health		
Clinical Phase	Phase II		
Study Rationale	The purpose of the PACE-Life trial is to develop and test the feasibility of an exercise intervention that combines group walking, activity tracking, and heart rate monitoring, and determine the effectiveness of this intervention on the physical and mental health for individuals with schizophrenia spectrum disorders.		
Study Objective(s)	
 
Feasibility- Can PACE-life be delivered within this treatment setting?
 
Tolerability- How well is PACE-life accepted by the subjects?
 
Intervention adherence
 
Evaluation of PACE-life
 
		
Test Article(s) (If Applicable)	Fitbits Charge 3 devices, worn on the wrist, will be utilized to track daily steps, minutes spent walking, and monitor HR throughout exercise sessions. These devices will also be used to facilitate the		
Study Design	individualized/home-based component and goal-setting.  This is a two arm (fitbit only vs. fitbit + exercise intervention group), randomized controlled trial with 56 subjects (multiple groups occurring consecutively ranging from 13-18 participants).		
Subject Population key criteria for Inclusion and Exclusion:	
 
Inclusion Criteria
 
DSM-V diagnosis of a SSD (Schizophrenia, Schizoaffective Disorder, Brief Psychotic Disorder, Schizophreniform Disorder, and Unspecified Schizophrenia Spectrum and Other Psychotic Disorder)
 
Between the ages of 18-65, both genders, and any ancestry;
 
IQ>70 and/or reading level at, or above the 4th grade. IQ will be assessed using the Wechsler Abbreviated Scale of Intelligence (WASI) and the Wide Range Achievement Test (WRAT).
 
No hospitalizations for psychiatric reasons in the last 3 months
 
Clinically stable (no psychiatric medication changes within the past month)
 
Are not already engaging in consistent moderate-intensity exercise (cutoff = 60 min/week for the past 6 months);
 
		

- 7. Present with no contra-indication to engage in regular moderate intensity exercise based on the American College of Sports Medicine guidelines. (If an individual answers yes to one item on the of the Physical Activity Readiness Questionnaire (PAR-Q), she/he will be asked to get clearance from a physician prior to participating in the study)
- 8. Willing and able to provide informed consent.

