A critical component of goal setting and attainment is being able to monitor progress, which can be achieved via physical activity tracking devices. Pedometer use leads to an increase in PA – they are considered acceptable and are highly useful for setting PA goals (83-85), which helps to facilitate changes in exercise behavior (86). In fact, pedometers are the most cost-effective means of increasing PA in the general population (87). In a systematic review of 26 studies, pedometer use resulted in significant increases in PA (26.9% over baseline) (70). With recent advances in sensor and Bluetooth technologies, new physical activity monitors have emerged and are currently commercially available (e.g., Fitbit), which also allow the measuring of walking intensity (e.g., through heart rate; See Section C.3.).

The model above illustrates how our proposed intervention, (PACE-Life) will lead to increased exercise and improved outcomes. Specifically, PACE-Life includes five primary components: home-based walking, group-based walking, activity tracking, goal-setting, and if-then plans, four of which impact the SDT basic needs and one of which enhances autonomous motivation. Specifically, homebased walking targets autonomy needs (as individuals can do this independently), group-based walking targets relatedness needs, and activity tracking and goal setting target competence needs. Satisfaction of each of the SDT needs leads to the intermediate target of increased autonomous motivation. PACE-Life subjects also form if-then plans which serve to enhance the impact of autonomous motivation (66, 67) and promote actual exercise behavior (56, 57). Engaging these intermediate targets in turn engenders the proximal outcomes of greater exercise participation (as measured by minutes spent walking per week and steps/day). Finally, increased exercise should lead to the improved primary outcome of CRF as well as improved secondary outcomes of loneliness, symptoms, resting heart rate, and systolic/diastolic blood pressure.

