### 4 STUDY DESIGN

During this phase of the trial, 56 subjects will be assigned to the fitbit only group (control) or the PACE-Life walking group (intervention). The exercise intervention, PACE-Life, will last for 16 weeks and includes both group walks and independent walks (done at a location of the subject's choosing). Subjects will be asked to complete a total of 5 in-person, or virtual assessments at screening, baseline, mid-point, post-test, and 1-month follow-up.

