### 4.1.2 FITBITS

All subjects will be provided with a Fitbit that is labeled with a subject number. All Fitbits are paired to a Fitbit account with the username ([contact]) and password (pacelife; or

PacelifeIDnumber!). Data from Fitbit devices can be synced to the corresponding account and accessed through Fitbit.com. Subjects will be provided information about their accounts should they want to look at the data but will be asked not to change any of the settings as we will be using data for tracking steps/day and minutes spent walking. No identifying information will be inputted in the Fitbit.com account for subjects.

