### **5.2 POWER ANALYSIS**

Power was estimated using Optimal Design Software. Assuming n=56 (28 per group), alpha=05, and the covariate accounted for 50% of variance, the proposed study has reasonable power to detect an effect size of .50 or larger in comparison of the groups at the end of treatment or follow-up and of .75 or larger in comparisons of the size of change over time. Thus, this study has good power to detect the types of differences detected in pilot study (ES of .50-1.03 in steps, .33-.40 in six-minute walk test, .54-.83 for BP and .52-1.09 for symptoms).

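### The effectiveness aim is worded for the whole PACE-Life package, but controls also get a Fitbit, so the randomised comparison estimates only what the other components add; the power conclusion in 5.2 makes no allowance for this and already fails for the 6MWT

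*Combined protocol and SAP*

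**What the plan says.** **Purpose.** After naming feasibility, the synopsis rationale describes an "exercise intervention that combines group walking, activity tracking, and heart rate monitoring, and determine the effectiveness of this intervention". The aims and hypotheses in section 3.1 likewise speak of the impact of PACE-Life and of what it will be associated with. Neither place names the comparator.

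**Package.** Section 1 says that "PACE-Life includes five primary components: home-based walking, group-based walking, activity tracking, goal-setting, and if-then plans". The same section supports tracking with a systematic review in which "pedometer use resulted in significant increases in PA (26.9% over baseline".

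**Arms.** The synopsis design line reads "This is a two arm (fitbit only vs. fitbit + exercise intervention group", and section 4 says that "56 subjects will be assigned to the fitbit only group (control) or the PACE-Life walking group (intervention". Section 4.1.2 adds: "All subjects will be provided with a Fitbit that is labeled with a subject number".

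**Power.** Section 5.2 takes 28 per group, alpha .05 and a covariate explaining 50% of variance. It claims reasonable power, without a percentage, for an effect of .50 between groups and .75 for change over time. It concludes: "Thus, this study has good power to detect the types of differences detected in pilot study". The pilot effects listed are .50-1.03 for steps, .33-.40 for the 6MWT, .54-.83 for blood pressure and .52-1.09 for symptoms.

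**Analysis.** The synopsis and section 5.1 plan mainly descriptive results with within-group effect sizes.

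**The concern.** A component given to both arms drops out of a randomised comparison. The protocol treats tracking as active: it is one of the five components, section 1 says that it serves competence needs, and the cited review links pedometer use to more activity. Steps and minutes walked, the proximal outcomes, are what a tracker would most plausibly move in the control arm.

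Two things are at stake. First, a small difference between arms could be read as failure of PACE-Life when both arms had improved; a reader of the synopsis rationale alone would not know that the comparison is over and above a Fitbit. Second, section 5.2 moves pilot effects into a comparison against a Fitbit arm without saying what the pilot compared. If those effects measure change under the whole package, they overstate the difference that this trial is set up to detect.

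**Working it through.** **1. What the comparison isolates.** Intervention arm: home walks, group walks, goal-setting and if-then plans, plus a Fitbit. Control arm: a Fitbit. The difference is the effect of the components other than the device, in people who all have one. The synopsis rationale and 3.1 do not state it this way.

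**2. Inputs (section 5.2).** n = 28 per arm, alpha = .05 (printed as 05), R² = .50. Sidedness is not stated; two-sided is assumed. No dropout allowance is stated and none is applied.

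**3. Formula.** Noncentral t with df = 56 − 3 = 53 and critical value 2.006. Noncentrality = d × √(n/2) / √(1 − R²) = d × √14 / √.50 = 5.29 × d.

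**4. The plan's own detectable effects.** For d = .50, noncentrality is 2.65 and power 73.8%. For d = .75 with no covariate adjustment, power is 78.7%. With no percentage in 5.2, an exact reproduction is not possible, but both fit the word reasonable. At 80% power and R² = .50 the detectable effect is 0.54.

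**5. Pilot effects, no discount.**

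| Outcome | Low end: power | High end: power |
|---|---|---|
| 6MWT (primary) | .33: 40% | .40: 55% |
| Steps | .50: 74% | 1.03: over 99% |
| Blood pressure | .54: 80% | .83: 99% |
| Symptoms | .52: 77% | 1.09: over 99% |

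Both 6MWT values lie below the .50 that 5.2 itself names as detectable.

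**6. Allowing for change in the Fitbit-only arm.** The documents give no standardised effect of tracking: the 26.9% comes without an SD and concerns activity only. A control change of 0.1 to 0.3 SD is therefore an assumption, subtracted from the pilot effect on the further assumption of a common standardiser.

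| Outcome, low end | No change | 0.1 SD | 0.3 SD |
|---|---|---|---|
| Steps | .50: 74% | .40: 55% | .20: 18% |
| Blood pressure | .54: 80% | .44: 63% | .24: 24% |
| Symptoms | .52: 77% | .42: 59% | .22: 21% |

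Upper ends at the full 0.3 SD: steps 1.03 − .30 = .73, 97%; blood pressure .83 − .30 = .53, 79%; symptoms 1.09 − .30 = .79, 98%. The result depends heavily on where in the pilot range the true effect lies.

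**The case against.** The case on the other side is substantial.

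- **The contrast is disclosed.** The synopsis states it as "two arm (fitbit only vs. fitbit + exercise intervention group", and an active comparator is a legitimate choice. This stands: the design is not at fault, only the wording of the aim, the hypotheses and the power conclusion.
- **A reader might infer that the added effect is certainly smaller than the pilot effects.** The documents do not support that. They give neither the pilot's comparator nor whether its effects are within or between groups. Section 4.1 says only that a twice-weekly schedule was tested. Likely smaller, under a stated condition, is as far as one can go.
- **A reader might take the 26.9% as the effect of a tracker on its own.** Section 1 does not say so, and it also recommends pedometers as an aid to goal-setting, which is a separate PACE-Life component. The documents give no tracking effect at all on blood pressure or symptoms, where the discount is weakest.
- **A reader might infer that the objective cannot be answered.** That goes too far. Feasibility, tolerability and adherence are unaffected, and the planned within-group effect sizes will describe change under the full package, though without a control. Section 5.1 lists no between-arm test, so misreading a null difference is a risk of interpretation, not of a specified analysis.
- **Having the device is not the same as receiving the whole tracking component.** The synopsis also ties the Fitbit to exercise sessions, home walks and goal-setting, so the two arms may use it differently. This stands, and it argues against listing precisely what the difference contains.

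None of this answers the 6MWT result, which needs no discount.

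**Conclusion.** The point holds as a mismatch between the stated aim and the randomised comparison, and as an unsupported power conclusion. The comparison estimates the effect of the other PACE-Life components added to a Fitbit; the synopsis rationale and 3.1 do not say so.

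The firmest number is for the primary outcome: about 40-55% power at the pilot's own 6MWT effects, under 5.2's inputs and a two-sided test. For steps, blood pressure and symptoms, the loss of power is conditional on the pilot effects being uncontrolled or against an inactive control, and on the assumed 0.1-0.3 SD change in controls. It bears on the lower part of each pilot range. It should not be read as a failure of power for every outcome named, since upper-end effects remain at 79-98% in the least favourable case shown.

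**What to change.** 1. In the synopsis and section 3.1, state the between-arm objective and hypotheses as the effect of the PACE-Life components added to a Fitbit, versus a Fitbit alone. Say that within-group change is an uncontrolled description of the package.
2. In section 5.2, delete the concluding sentence that begins with Thus. Alternatively, restate power by outcome, giving the 6MWT at about 40-55% and a sensitivity range for change in the Fitbit-only arm (for example 0.1, 0.2 and 0.3 SD, labelled as assumptions).

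The cost is a protocol text change and a less favourable power statement. The design, sample size and data collection do not change.

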### **Exclusion Criteria**

 Pregnant women will be excluded because pregnancy alters autonomic and immune responsiveness, increase weight gain, and can influence heart rate.

### **Number Of Subjects**

56 individuals with schizophrenia spectrum disorders

### **Study Duration**

Each subject's participation will last 5 months, 4 months of intervention and a 1 month follow-up

### Study Phases Screening Study Treatment Follow-Up

Pre- Screening- Will be completed prior to the first in-person visit via a telephone screen for study eligibility.

Screening- Subjects who are deemed eligible will be brought on site, or virtually via HIPAA-compliant Zoom video call, to obtain consent and complete the screening assessments (Demographics, WASI/WRAT, a licensed physician will complete a medical history and physical exam, PAR-Q.

Baseline, Mid-point, Post-test, and 1-Month Follow-up-Subjects will complete the Demographics, Minutes Spent Walking, the Positive and Negative Syndrome Scale (PANSS), the Short Form International Physical Activity Questionnaire (IPAQ), Steps/day, Cardiorespiratory fitness (CRF)- CRF will be measured using the 6minute walk test (6MWT), Chair-Rise Task, 2-minute Step Test, Selfdetermination Basic Needs, the Basic Psychological Need Scale-in General, the Basic Psychological Needs in Exercise Scale (BPNES), Resting Systolic/Diastolic Blood Pressure and resting heart rate (RHR), autonomous motivation will be measured with the Behavioral Regulation in Exercise Questionnaire-2 (BREQ-2), enjoyment of walking will be measured with the Physical Activity Enjoyment Scale (PACES), the UCLA Loneliness Scale, Weight, BMI, and Waist/hip Circumference: study intervention/experimental treatment. CRF will also be calculated using an equation by Jackson, A. S., et al. 1990 (119) that includes recent weight and height for the calculation of BMI, gender, self-reported physical activity level, and age.

At the baseline assessment, subjects will be provided with a Fitbit wristband and instructed how to use it. At the conclusion of the trial, investigators will administer a brief questionnaire to the subjects regarding satisfaction and acceptability.

Study Treatment- Walking groups will occur twice per week for 30 minutes. The intensity of both group walks and home-based walks will increase throughout this intervention in a stepwise fashion to create an exercise dose response to maximize impact on CRF. During the COVID-19 pandemic, participants will participate in group walks via Zoom video meetings twice per week, starting at 15-minute sessions and progressing to 30-minute sessions, where group leaders will lead participants through exercise sessions.

### **Efficacy Evaluations**

Primary outcome- 6MWT will be used to measure CRF during which individuals will be asked to walk continuously for six minutes on a flat, indoor surface around cones (separated by 100ft). Supplemental CRF measures will also be used. CRF will be calculated using an equation by Jackson, A. S., et al. 1990 that includes recent weight and height for the calculation of BMI, gender, self-reported physical activity level, and age. Finally, participants will complete the Chair-Rise Task, and the 2-minute Step Test to measure CRF.

Secondary outcomes- Psychological- UCLA Loneliness Scale will be used to assess subjective feelings of loneliness. The PANSS will be utilized to assess psychiatric symptoms.

Secondary outcomes- Biological- We will measure weight, BMI, and waist circumference at all in-person assessments. We will examine these characteristics to determine if they changed as a result of increasing exercise. Resting Systolic/Diastolic Blood Pressure and RHR will also be assessed following standardized procedures.

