### 2.2 SUBJECTS

Based on the grave health concerns, physical inactivity, and growing urgent calls for action in individuals with psychotic disorders (116, 117), 56 study subjects will be recruited from various clinics in the Durham, Carrboro, Chapel Hill, and Raleigh area including, the UNC Schizophrenia Treatment and Evaluation Program (STEP) clinic in Raleigh and Carrboro, the Outreach and Support Intervention Services (OASIS) program in Chapel Hill, Carolina Behavioral Care, Club Nova, and Threshold. All subjects will have a primary diagnosis of a schizophrenia spectrum disorder. To obtain an estimate of IQ and to rule out any individuals with possible mental retardation, we will administer the WASI, which is comprised of Matrix Reasoning, Vocabulary, Similarities, and the Block Design subtests. During the COVID-19 pandemic, we will also administer the WRAT to test the reading level of participants. Additional demographic and clinical information that will be collected as self-report for possible use as covariates includes: 1) demographics: age, sex, ancestry, education, parent education; 2) health: smoking, substance use, current medications, duration of outpatient treatment, diet, physical activity, height, weight, BMI, and waist and hip circumference.

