### 3.1 OUTCOMES

The central hypothesis is that an intervention that increases physical activity as measured by minutes spent walking (at the prescribed intensity) and steps/day will result in improved health and lowered risk for premature mortality as evidenced by superior CRF (primary outcome), and on a variety of secondary outcomes (e.g. blood pressure). Guided by strong preliminary data and grounded in SDT, this hypothesis will be tested via three specific aims:

- 1. To develop a manual-based walking intervention for individuals with SSDs: PACE-Life. The manual will include guidelines for goal setting and translating intentions into behaviors (i.e., "if-then" plans), instructions for the group-based walking activity and home-based walking activity (which includes Fitbits), and increasing exercise intensity in a step-wise manner.
- 2. To examine the feasibility of implementing PACE-life at a community mental health clinic, and in a home-based virtual capacity, in a randomized controlled trial of 56 individuals with SSDs.
- 3. We will also examine the impact of PACE-life on intermediate targets (autonomous motivation and SDT needs), proximal outcomes (minutes spent walking and steps/day), the primary outcome of CRF, and secondary outcomes.

We hypothesize that PACE-life will be associated with:

- Improved proximal and primary outcomes including greater minutes/week spent walking and steps/day and increased CRF at mid-treatment (3 months), post-test (6 months), and one-month follow-up;
- Decreases in secondary outcomes including loneliness, SSD symptoms, resting heart rate, and blood pressure at mid-point, post-test, and one-month follow-up.
- Higher levels of theoretically-relevant, intermediate targets (autonomous motivation and SDT needs) at mid-treatment, post-test, and one-month follow-up.

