### 5 STATISTICAL ANALYSES

### **5.1 DATA ANALYTIC PLAN**

Feasibility will be defined by our ability to meet our recruitment targets (56 people), frequency of engagement in the intervention by participants (group attendance and activity tracking/home-based adherence), and feedback on the intervention from participants. Feedback from participants will be incorporated into modifying the manual for the RCT and/or future interventions.

Analyses of intermediate and primary outcomes will primarily be descriptive in nature. We will calculate means, standard deviations, and within-group effect sizes of intermediate targets (SDT needs and autonomous motivation), proximal outcomes, including minutes spent walking, and steps/day, the primary outcome of CRF, and the secondary outcomes including RHR, blood pressure, loneliness, and symptoms. Further, we will calculate the percentage of the sample meeting the threshold for clinically significant changes in our outcomes of 6MWT, steps/day, and minutes spent walking to determine whether these changes are clinically meaningful. Finally, we will explore the relationship between baseline IQ, treatment adherence and outcome improvement so as to determine if cognitive functioning is associated with treatment response.

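### Does the equation-based fitness estimate make the exploratory adherence–outcome analysis circular?

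*Combined protocol and SAP*

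**What the plan says.** In the synopsis (Efficacy Evaluations) and in section 4.2.2, the 6MWT is the primary CRF measure. Three further measures are labelled supplemental: the chair-rise task, the 2-minute step test, and a published equation that "includes recent weight and height for the calculation of BMI, gender, self-reported physical activity level, and age". The title of the cited source (reference 119) indicates that the prediction is made without an exercise test.

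Section 5.1 is mainly descriptive. It lists "the primary outcome of CRF, and the secondary outcomes including RHR, blood pressure, loneliness, and symptoms", giving CRF without its instrument. It then plans the percentage of participants with clinically significant change in three named outcomes: 6MWT, steps/day and minutes walking. In the next sentence "we will explore the relationship between baseline IQ, treatment adherence and outcome improvement", with the stated aim of learning whether cognitive functioning goes with treatment response. Earlier in the section, feasibility includes "frequency of engagement in the intervention by participants (group attendance and activity tracking/home-based adherence".

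The equation's two changeable inputs are described unevenly. Section 2.2 puts physical activity and weight among items that "will be collected as self-report for possible use as covariates". The synopsis says "We will measure weight, BMI, and waist circumference at all in-person assessments". Section 4.2.2 has weight taken at every assessment on the clinic's scale, while section 4 allows virtual assessments. Section 4.2.2 also collects the IPAQ, and no passage says which activity item feeds the equation.

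**The concern.** A prediction equation that takes reported activity as an input cannot give independent evidence that activity improved fitness. Someone who walks more and says so will score higher on it whether or not aerobic capacity changed. Adherence in this trial is largely activity done, so correlating adherence with change in the equation value puts the same behaviour on both axes. Section 5.1 does not list the outcomes in its adherence analysis and excludes none, and it says CRF where several CRF measures exist.

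At stake would be a claim that adherent participants became fitter when the data show only that they reported more activity. The worry grows if weight is not updated at a virtual visit, because reported activity would then be almost the only input that moves. It could also seem to reach the trial's main argument, that "increased exercise should lead to the improved primary outcome of CRF".

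**Working it through.** The plan gives no figure on this point, so there is none to reproduce. The check has four steps.

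**1. What can move in the equation value.** Within a participant, gender and height are fixed. Age moves 5/12 = 0.42 year over the 5 months in the synopsis, or 7/12 = 0.58 year if section 3.1's post-test at 6 months plus one month is used. Change therefore comes from weight and reported activity. This part of the concern is correct.

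**2. How large the built-in correlation could be.** Suppose true fitness does not change and the equation is additive. Write the change as E = bP + cW, where P is change in reported activity and W is change in BMI, uncorrelated with P and with adherence A. Then

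corr(A, E) = ρ × √s,

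where ρ = corr(A, P) and s is the share of the variance of E that comes from P. Neither ρ nor s is in the documents, so both are assumed over a range:

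| ρ (assumed) | s (assumed) | induced r |
|---|---|---|
| 0 | any | 0 |
| 0.2 | 0.25 | 0.2 × 0.500 = 0.10 |
| 0.5 | 0.50 | 0.5 × 0.707 = 0.35 |
| 0.7 | 0.90 | 0.7 × 0.949 = 0.66 |

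If weight is not updated, s = 1 and r = ρ. That is an identity and says nothing about what ρ would be in this trial. Adherence comes from attendance, home-based adherence and Fitbit usage, none of it described as self-report. The overlap is therefore one of construct, not a shared measurement. The assumption that weight change is unrelated to adherence is also doubtful, since the synopsis examines whether weight changed because of more exercise.

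**3. Whether the plan uses the value this way.**
- The equation value is supplemental wherever its status is given; section 4.2.2 names the 6MWT as primary.
- The sentence just before the adherence analysis in section 5.1 names its outcomes, and the equation value is not among them. That list governs the threshold percentages, but it is the nearest guide to what outcome improvement means.
- The adherence analysis is exploratory and aimed at baseline IQ, which is not an equation input.
- The central hypothesis in section 3.1 concerns "an intervention that increases physical activity as measured by minutes spent walking" and steps/day, both taken from the Fitbit under section 4.2.2, and CRF as primary outcome, which is the 6MWT. Neither side of that hypothesis uses the equation.

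**4. Whether excluding the value would cure the overlap.** Steps/day and minutes walking are named outcomes and overlap with tracked adherence more directly than the equation value does. Removing the equation value would leave that overlap in place. Restricting the analysis to 6MWT distance would also drop symptoms, loneliness, blood pressure and resting heart rate, which have no such overlap.

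**The case for a change.** The best argument for a change is that silence permits the misuse and a few sentences would prevent it. The synopsis describes the equation under its primary-outcome heading, section 5.1 says only CRF, and a report could present the equation value as a fitness gain among adherers. With ρ = 0.5 and s = 0.5, the induced r of 0.35 would pass a nominal two-sided 5% test (critical r 0.374 for n = 28, 0.263 for n = 56) in about 47% of samples of 28 and 78% of samples of 56. Naming 6MWT distance would close that route.

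Much of this stands as description: reported activity is an input, the outcome list is unstated, the activity item is unnamed, and the weight wording differs between sections. The rejection rates carry little weight. Section 5.1 specifies no significance test of adherence against outcome, and both inputs are assumed; at ρ = 0.2 and s = 0.25 the rates fall to about 8% and 11%. The sample of 56 is also strained, because the control arm receives a Fitbit only and has no group sessions to attend. Finally, weight, IPAQ and Fitbit data are collected alongside, so a reader can see what moved the equation value.

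**Conclusion.** No change to the plan is needed. The equation value would be a poor outcome to set against adherence, and an analyst who did so would get a partly built-in association. Its size cannot be obtained from the documents: roughly 0.10 to 0.66 over the assumed ranges, and zero if reported activity is unrelated to adherence. The plan does not state that use. The 6MWT primary result, the threshold percentages and the central hypothesis do not depend on the equation.

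The remaining gap is missing detail in an exploratory analysis within a mainly descriptive plan. The sensible reading is available from the text: where CRF is the outcome, it is 6MWT distance, and the equation value is reported as a supplemental estimate. The uneven wording on weight and the unnamed activity item are housekeeping matters that affect only that estimate's interpretation. This conclusion assumes that analysts follow the stated hierarchy of CRF measures. It would need revisiting only if a report rested a claim of improved fitness on the equation value.
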